Appendix B. Bohan & Peter (1975) Diagnostic Criteria for Polymyositis and Dermatomyositis¹²

Diagnostic Criteria for Polymyositis and Dermatomyositis (Bohan & Peter)

1. Symmetric proximal muscle weakness determined by physical examination.
2. Elevation of serum skeletal muscle enzymes (particularly creatine kinase and aldolase), serum glutamate| oxaloacetate, pyruvate transaminases, and lactate dehydrogenase.
3. The electromyographic triad of short, small, polyphasic motor unit potentials; fibrillations, positive sharp waves, and insertional irritability; and bizarre, high-frequency repetitive discharges.
4. Muscle biopsy specimen abnormalities of degeneration, regeneration, necrosis, phagocytosis, and interstitial mononuclear infiltrate.
5. Typical skin rash of dermatomyositis, including a heliotrope rash, Gottron sign, and Gottron papules.

Using these criteria, polymyositis is defined as definite (all of criteria 1-4), probable (any three of criteria 1-4), or possible (any two of criteria 1-4). Dermatomyositis is defined as definite (5 plus any three of criteria 1-4), probable (5 plus any two of criteria 1-4), or possible (5 plus any one of criteria 1-4).

Appendix C.: Liver Chemistry Stopping and Follow Up Criteria

Liver chemistry stopping criteria

Liver chemistry stopping and increased monitoring criteria have been designed to assure subject safety and evaluate liver event etiology (in alignment with the FDA premarketing clinical liver safety guidance). These criteria have been amended for this myositis protocol to accommodate for a specific population of myositis patients with ALT/AST abnormalities as a result of muscle injury. Baseline bilirubin, GGT and INR must be at or near normal. (Note: ULN – upper limit of normal as determined by the reference range of the local lab. All liver toxicities must be reported to the Sponsor (Northwell Health). Subjects that meet liver stopping criteria MUST be reported to GSK within 24 hours.)

- ALT Absolute:
 - ALT \geq 8xULN (without elevated CPK, and/or myoglobin)
 - If ALT \geq 8xULN **and serum GGT \geq 3xULN** (irrespective of CPK and/or myoglobin values)
- ALT Increase:
 - ALT \geq 5xULN but $<$ 8xULN (without elevated CPK, and/or myoglobin) **and GGT \geq 3xULN**, persists for \geq 2 weeks
 - ALT \geq 3xULN but $<$ 5xULN (without elevated CPK, and/or myoglobin) **and GGT \geq 3xULN**, persists for \geq 4 weeks
- Bilirubin: ALT \geq 3xULN and bilirubin \geq 2xULN ($>$ 35% direct bilirubin) ^{a, b}
- INR: ALT \geq 3xULN and INR $>$ 1.5, if INR measured ^b
- Cannot Monitor:
 - ALT \geq 5xULN but $<$ 8xULN (without elevated CPK, and/or myoglobin) **and GGT \geq 3xULN** and labs cannot be monitored weekly for \geq 2 weeks
 - ALT \geq 3xULN but $<$ 5xULN (without elevated CPK, and/or myoglobin) **and GGT \geq 3xULN** and labs cannot be monitored weekly for \geq 4 weeks
- Symptomatic: ALT \geq 3xULN (without elevated CPK, and/or myoglobin) **and GGT \geq 3xULN** associated with symptoms (new or worsening) believed to be related to liver injury or hypersensitivity ^c
 - a) Serum bilirubin fractionation should be performed if testing is available. If serum bilirubin fractionation is not immediately available, discontinue study treatment for that subject if bilirubin \geq 2xULN. Additionally, if serum bilirubin fractionation testing is unavailable, **record presence of detectable urinary bilirubin on dipstick**, indicating direct bilirubin elevations and suggesting liver injury.
 - b) All events of ALT \geq 3xULN (without elevated CPK, and/or myoglobin) **and GGT \geq 3xULN**

- c) All events of ALT \geq 3xULN (without elevated CPK, and/or myoglobin) **and** bilirubin \geq 2xULN ($>35\%$ direct bilirubin) or ALT \geq 3xULN **and** INR >1.5 , if INR measured which may indicate severe liver injury (possible 'Hy's Law'), **must be reported as an SAE (excluding studies of hepatic impairment or cirrhosis)**; INR measurement is not required and the threshold value stated will not apply to subjects receiving anticoagulants
- d) New or worsening symptoms believed to be related to liver injury (such as fatigue, nausea, vomiting, right upper quadrant pain or tenderness, or jaundice) or believed to be related to hypersensitivity (such as fever, rash or eosinophilia)

Required Actions and Follow up Assessments following ANY Liver Stopping Event

Actions:

- Immediately discontinue study treatment
- Report the event to GSK within 24 hours
- Complete the liver event CRF and complete SAE data collection tool if the event also meets the criteria for an SAE
 - All events of ALT \geq 3xULN (without elevated CPK, and/or myoglobin) **and elevated GGT \geq 3xULN or**
 - All events of ALT \geq 3xULN (without elevated CPK, and/or myoglobin) **and bilirubin \geq 2xULN ($>35\%$ direct bilirubin) or**
 - All events of ALT \geq 3xULN (without elevated CPK, and/or myoglobin) **and INR >1.5** , if INR measured which may indicate severe liver injury (possible 'Hy's Law'), must be reported as an SAE (excluding studies of hepatic impairment or cirrhosis); INR measurement is not required and the threshold value stated will not apply to subjects receiving anticoagulants)
- Perform liver event follow up assessments
- Monitor the subject until liver chemistries resolve, stabilize, or return to within baseline (see MONITORING below)
- Do not restart/rechallenge subject with study treatment unless allowed per protocol and GSK Medical Governance approval is granted

MONITORING:

For bilirubin or INR criteria:

- Repeat liver chemistries (include ALT, AST, GGT, alkaline phosphatase, bilirubin) and perform liver event follow up assessments within **24 hrs**
- Monitor subjects twice weekly until liver chemistries resolve, stabilize or return to within baseline
- A specialist or hepatology consultation is recommended

For All other criteria:

- Repeat liver chemistries (include ALT, AST, GGT, alkaline phosphatase, bilirubin) and perform liver event follow up assessments within 24-72 hrs
- Monitor subjects weekly until liver chemistries resolve, stabilize or return to within baseline

FOLLOW UP ASSESSMENTS:

- Viral hepatitis serology (Includes: Hepatitis A IgM antibody; Hepatitis B surface antigen and Hepatitis B Core Antibody (IgM); Hepatitis C RNA; Cytomegalovirus IgM antibody; Epstein-Barr viral capsid antigen IgM antibody (or if unavailable, obtain heterophile antibody or monospot testing); Hepatitis E IgM antibody)

For subjects who have had IVIG in the past and with Hep B core IgG pos and Hep B sAB pos. additional safety monitoring procedures must be followed. HBVDNA testing must be done every 2 months and when ALT or AST elevations increase $> 2.5 \times \text{ULN}$ during the study

-
- Blood sample for pharmacokinetic (PK) analysis, obtained within [insert time interval recommended by clinical pharmacokinetics representative] after last dose (PK sample may not be required for subjects known to be receiving placebo or non-GSK comparator treatments.) Record the date/time of the PK blood sample draw and the date/time of the last dose of study treatment prior to blood sample draw on the CRF. If the date or time of the last dose is unclear, provide the subject's best approximation. If the date/time of the last dose cannot be approximated OR a PK sample cannot be collected in the time period indicated above, do not obtain a PK sample. Instructions for sample handling and shipping are in the SRM. Not required for single-dose studies
- Serum GGT, creatine phosphokinase (CPK) and lactate dehydrogenase (LDH).
- Fractionate bilirubin, if total bilirubin $\geq 2 \times \text{ULN}$
- Obtain complete blood count with differential to assess eosinophilia
- Record the appearance or worsening of clinical symptoms of liver injury, or hypersensitivity, on the AE report form
- Record use of concomitant medications on the concomitant medications report form including acetaminophen, herbal remedies, other over the counter medications
- Record alcohol use on the liver event alcohol intake case report form

For bilirubin or INR criteria:

- Anti-nuclear antibody, anti-smooth muscle antibody, Type 1 anti-liver kidney microsomal antibodies, and quantitative total immunoglobulin G (IgG or gamma globulins).
- Serum acetaminophen adduct HPLC assay (quantifies potential acetaminophen contribution to liver injury in subjects with definite or likely acetaminophen use in the preceding week [James, 2009]). NOTE: not required in China

- Liver imaging (ultrasound, magnetic resonance, or computerised tomography) and /or liver biopsy to evaluate liver disease: complete Liver Imaging and/or Liver Biopsy CRF forms.

Increased monitoring criteria with continued therapy

Criteria

- For subjects who have had IVIG in the past, additional HBVDNA testing must be completed when ALT or AST elevations increase to $>2.5\times\text{ULN}$ during the study
- If ALT $\geq 5\times\text{ULN}$ and $<8\times\text{ULN}$ (without elevated CPK, and/or myoglobin) and bilirubin $<2\times\text{ULN}$ without symptoms believed to be related to liver injury or hypersensitivity, and who can be monitored weekly for 2 weeks **OR**
- ALT $\geq 3\times\text{ULN}$ and $<5\times\text{ULN}$ (without elevated CPK, and/or myoglobin) and bilirubin $<2\times\text{ULN}$ without symptoms believed to be related to liver injury or hypersensitivity, and who can be monitored weekly for 4 weeks
- If ALT $\geq 5\times\text{ULN}$ and $<8\times\text{ULN}$ (without elevated CPK, and/or myoglobin) and **GGT is $\geq 1.5\times\text{ULN}$** to $< 3\times\text{ULN}$ without symptoms believed to be related to liver injury or hypersensitivity, and who can be monitored weekly for 2 weeks **OR**
- ALT $\geq 3\times\text{ULN}$ and $<5\times\text{ULN}$ (without elevated CPK, and/or myoglobin) and **GGT is $\geq 1.5\times\text{ULN}$** to $< 3\times\text{ULN}$ without symptoms believed to be related to liver injury or hypersensitivity, and who can be monitored weekly for 4 weeks

Required Actions

- Notify the Sponsor (Northwell Health) and GSK within 24 hours of learning of the abnormality to discuss subject safety.
- Subject can continue study treatment
- Subject must return weekly for repeat liver chemistries (ALT, AST, GGT, alkaline phosphatase, bilirubin) until they resolve, stabilize or return to within baseline
- If at any time subject meets the liver chemistry stopping criteria, proceed as described above for Required Actions and Follow up Assessments following ANY Liver Stopping Event
- If ALT decreases from ALT $\geq 5\times\text{ULN}$ and $<8\times\text{ULN}$ to $\geq 3\times\text{ULN}$ but $<5\times\text{ULN}$ (without elevated CPK, and/or myoglobin) and **GGT is $\geq 1.5\times\text{ULN}$** to $< 3\times\text{ULN}$, continue to monitor liver chemistries weekly.
- If, after 4 weeks of monitoring, ALT $<3\times\text{ULN}$ (without elevated CPK, and/or myoglobin) **and** bilirubin $<2\times\text{ULN}$ **and/or** GGT is $<2\times\text{ULN}$, monitor subjects twice monthly until liver chemistries normalize or return to within baseline.

NOTE: If any of above rules are met, but the investigator feels that laboratory changes are due to myositis activity and not liver injury, the investigator will discuss with the Sponsor (Northwell Health) and GSK to determine the continuation of the subject in the protocol.

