- h. All events of possible drug-induced liver injury with **hyperbilirubinaemia** defined as **ALT \geq 3xULN** (without elevated CPK, and/or myoglobin) **and bilirubin \geq 2xULN ($>35\%$ direct)**

- i. All events of possible liver injury with **increased INR** defined as **ALT \geq 3xULN** (without elevated CPK, and/or myoglobin) **and INR >1.5** . If INR measured termed 'Hy's Law' events (INR measurement is not required and the threshold value stated will not apply to patients receiving anticoagulants).

NOTE: bilirubin fractionation is performed if testing is available. If testing is unavailable, record presence of detectable urinary bilirubin on dipstick indicating direct bilirubin elevations and suggesting liver injury. If testing is unavailable and a subject meets the criterion of total bilirubin \geq 2xULN, then the event is still reported as an SAE. If INR is obtained, include values on the SAE form. INR elevations >1.5 suggest severe liver injury. (See Appendix C).

NOTE:

ULN (Upper Limit of Normal) as determined by the reference range of the local lab

All liver toxicities must be reported to the Sponsor (Northwell Health) and GSK.

Subjects that meet liver stopping criteria (See Appendix C) MUST be reported to GSK within 24 hours.

In the case of a LIVER STOPPING EVENT, follow up assessments should be completed (see Appendix C).

Laboratory and Other Safety Assessment Abnormalities Reported as AEs and SAEs: Any abnormal laboratory test results (hematology, clinical chemistry, or urinalysis) or other safety assessments (e.g., ECGs, radiological scans, vital signs measurements), including those that worsen from baseline, and felt to be clinically significant in the medical and scientific judgment of the investigator are to be recorded as AEs or SAEs.

NOTE: However, any clinically significant safety assessments that are associated with the underlying disease, unless judged by the investigator to be more severe than expected for the subject's condition, are **not** to be reported as AEs or SAEs.

Adverse Events of Special Interest: The following AEs should be monitored closely and reported to the study sponsor immediately.

1. **Serious hypersensitivity reaction or Infusion Reactions** (See Section: Study Drug Administration and Considerations)

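### Bilirubin and INR liver stopping events carry no CPK condition, but with raised CPK or myoglobin the bilirubin event is not automatically an SAE, and the SAE texts for INR are inconsistent

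*Combined protocol and SAP*

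**What the plan says.** **Stopping.** The Appendix C list has a bilirubin line, "Bilirubin: ALT \geq 3xULN and bilirubin \geq 2xULN ($>$ 35% direct bilirubin"), and an INR line, "INR: ALT \geq 3xULN and INR $>$ 1.5, if INR measured". Neither mentions CPK or myoglobin. Appendix C says that its criteria were amended "to accommodate for a specific population of myositis patients with ALT/AST abnormalities as a result of muscle injury". A closing note lets the investigator discuss continuation with the sponsor and GSK if the changes are thought to come from myositis.

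**SAE status, bilirubin.** Item h of the SAE definition (Safety Considerations and Adverse Events) applies to ALT ≥3×ULN "without elevated CPK, and/or myoglobin) and bilirubin \geq 2xULN". The action list for liver stopping events and note c), both in Appendix C, carry the same qualifier.

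**SAE status, INR.** Item i reads "All events of possible liver injury with increased INR defined as ALT \geq 3xULN (without elevated CPK, and/or myoglobin"), and the action list agrees. Note c) puts the qualifier on its bilirubin half, then continues "or ALT \geq 3xULN and INR >1.5 , if INR measured which may indicate severe liver injury", and requires SAE reporting.

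**Two related notes.** On bilirubin fractionation: "If testing is unavailable and a subject meets the criterion of total bilirubin \geq 2xULN, then the event is still reported as an SAE". On laboratory abnormalities, sites are told not to report as AEs or SAEs "any clinically significant safety assessments that are associated with the underlying disease, unless judged by the investigator to be more severe than expected" for that patient.

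**The concern.** The plan treats ALT ≥3×ULN with raised direct bilirubin or raised INR as a liver event serious enough to stop drug, and describes it as possible Hy's Law. When CPK or myoglobin is also raised, the same event can fall outside the automatic SAE definition.

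This matters in myositis. A raised muscle enzyme is one of the six core set measures of active disease, and DM patients who miss the MMT criterion must have one. That criterion also accepts ALT or AST, so it does not show how many patients will have raised CPK.

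What could be lost is the 24-hour SAE report to the local IRB, the onward report to the FDA (Adverse Event and Serious Adverse Event Reporting), and a place in the SAE tally (secondary endpoint i, specific aim 11). The fallback is the general SAE criteria a to f. Item f rests on judgement, and the laboratory note on underlying disease may push that judgement towards not reporting when CPK is high.

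**Working it through.** The check is a comparison of texts. The plan states no figure to reproduce.

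**Step 1. Is the missing qualifier on the two stopping lines distinctive?** Count the stopping lines in Appendix C and those that exclude raised CPK/myoglobin.

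| Group | Lines | With the exclusion |
|---|---|---|
| ALT absolute | 2 | 1 |
| ALT increase | 2 | 2 |
| Bilirubin | 1 | 0 |
| INR | 1 | 0 |
| Cannot monitor | 2 | 2 |
| Symptomatic | 1 | 1 |
| Total | 9 | 6 |

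The three lines without it are bilirubin, INR, and ALT ≥8×ULN with GGT ≥3×ULN. Only the last says in words that CPK is irrelevant. For bilirubin and INR this follows from the absence of a condition.

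**Step 2. SAE status by CPK state.** Take ALT ≥3×ULN, fractionation available, INR measured and no anticoagulant. Raised means CPK or myoglobin above normal.

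| Event | CPK state | Stop | Item h or i | Action list | Note c) | SAE texts met |
|---|---|---|---|---|---|---|
| Bilirubin ≥2×ULN, >35% direct | not raised | yes | yes | yes | yes | 3 of 3 |
| Bilirubin ≥2×ULN, >35% direct | raised | yes | no | no | no | 0 of 3 |
| INR >1.5 | not raised | yes | yes | yes | yes | 3 of 3 |
| INR >1.5 | raised | yes | no | no | yes, as written | 1 of 3 |

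**Step 3. The fractionation note.** Read literally, it makes bilirubin ≥2×ULN an SAE when fractionation is unavailable, with no CPK condition. A patient with raised CPK and a confirmed direct fraction above 35% would then be classified less strictly than one whose fraction is unknown. If the note is read as replacing only the fraction in item h, this oddity disappears, but the gap in Step 2 remains.

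**Step 4. What happens whatever the SAE status.** Drug stops, GSK is told within 24 hours, the liver event form is completed, and chemistries are repeated within 24 hours for the bilirubin and INR criteria. All liver toxicities go to the sponsor, and abnormal liver enzymes are an event of special interest. The automatic SAE classification is the only part missing.

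**Step 5. Size.** The documents give no event rate and no share of patients with raised CPK, so no frequency can be derived. Exclusion criterion 17 limits entry bilirubin to 1.25×ULN and INR to 1.2 off anticoagulants. A patient at those limits needs a bilirubin rise of at least 2.0/1.25 = 1.6-fold, or an INR rise above 1.5/1.2 = 1.25-fold. With 30 patients planned, such events are likely to be few. With 15 per arm, one reclassified patient with no other SAE moves that arm's SAE proportion by 1/15 = 6.7 percentage points.

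**Step 6. After the fix.** With the qualifier deleted from items h and i, the two action-list lines and note c), all four rows of the Step 2 table read 3 of 3.

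**The case against.** **Stopping and seriousness are separate tests.** The action list asks for the SAE form only if SAE criteria are also met, so a stopping rule wider than the SAE rule is expected. ALT ≥8×ULN with normal CPK, for example, stops drug, but item g makes it an SAE only with GGT ≥3×ULN. This stands. The three bilirubin texts agree with one another, so a reader who infers a contradiction there goes too far.

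**The qualifier has a reason.** It follows ALT in each text and discounts ALT that may come from muscle, which is the stated purpose of the amendment. This also stands, and it would be wrong to call the qualifier unexplained. The purpose is limited to ALT and AST, however. Muscle injury does not explain a rise in direct bilirubin or INR, and the stopping lines already treat those as liver events without asking about CPK.

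**The INR texts do not strictly conflict.** Each says what is an SAE, and none says that a raised-CPK event is not one. A site that reports under note c) satisfies all three. Alternatively, the qualifier at the start of note c) may carry across the 'or', although restating ALT without it makes that reading weak. The note markers also look shifted: the bilirubin and INR lines point to b, while their SAE text is in c). That may come from drafting or from reading the PDF, and nothing here rests on the lettering. What remains is inconsistent wording that two sites could apply differently.

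**There is a fallback.** Item f permits an SAE by judgement. If muscle disease does not explain the bilirubin or INR rise, the underlying-disease exemption gives little cover. This is fair, but items g to i exist so that liver events do not depend on judgement.

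**Conclusion.** The point holds as a minor safety-reporting gap. With CPK or myoglobin raised, ALT ≥3×ULN with bilirubin ≥2×ULN (>35% direct) is a stopping event but not automatically an SAE. With INR >1.5, automatic SAE status depends on which text is followed. The first is a mismatch of scope and the second an inconsistency.

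A reader might infer that patients with possible Hy's Law would stay on drug, or that nobody would be told. The documents do not support that. Drug stops and GSK and the sponsor are informed whatever the CPK, and the closing note of Appendix C allows only a discussion of continuation. Nor does any efficacy result, power or alpha change. The effect is confined to the automatic SAE route (the 24-hour IRB report and the onward FDA report) and the SAE count.

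The conclusion assumes that 'raised' means either marker above normal, that fractionation is available, that INR is measured, and that the patient is not on an anticoagulant. No frequency is claimed.

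**What to change.** Delete the parenthesis about CPK and myoglobin in five places: SAE item h, SAE item i, the bilirubin line of the Appendix C action list, its INR line, and note c). Leave the bilirubin and INR stopping rules as they are. Cases thought to be myositis keep the closing-note discussion of continuation, which does not bear on SAE classification.

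The cost is a wording change and possibly a few more expedited reports, each for an event that already stops drug and goes to GSK within 24 hours.

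A separate option: ALT ≥8×ULN with GGT ≥3×ULN stops drug irrespective of CPK, while item g excludes raised CPK. If the sponsor wants that event to be an SAE too, item g, its action-list line and note b) should change together.

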- iii. Patients who previously received IVIG and have positive core antibody (Hepatitis B coreAb) and negative Hep B surface antibodies with or without the presence of positive HBVDNA by PCR
- Note: Patients who previously received IVIG and with Hep B core IgG pos and Hep B sAB pos. are allowed to be enrolled but additional safety monitoring procedures must be followed on these patients – please see Appendix C: Follow Up Assessments. The table below describes which types of patients would be eligible based on different Hep B core/surface ab positivity.

Hep Bs ag	+	-/+	-/+	-	-	-
Hep B s ab	-/+	+	-/+	-	-	+
Hep B core ab IgM	-/+	+	-/+	-	-	-
Hep B core ab IgG	-/+	-/+	-/+	+	+	+
					repeat	
Hep B by PCR	-/+	-/+	+	-	-	-
STATUS:	Not eligible	Not eligible	Not eligible	Not eligible	Eligible	Eligible

- b. Hepatitis C:
 - c. Positive hepatitis C antibody with confirmatory hepatitis C viral load by PCR.
- 17. Clinically significant elevation of GGT ($>1.5 \times \text{ULN}$), bilirubin ($>1.25 \times \text{ULN}$, direct 35%), or INR (>1.2 , excluding patients on anti-coagulant therapies) or other clinically significant abnormal laboratory value in the opinion of the investigator.
- 18. Have current drug or alcohol abuse or dependence, or a history of drug or alcohol abuse or dependence within 364 days prior to Day 0.
- 19. Have evidence of serious suicide risk including any history of suicidal behaviour in the last 6 months and/or any suicidal ideation in the last 2 months or who in the investigator's judgment, pose a significant suicide risk.
- 20. Have any concurrent significant medical or psychiatric illness that the investigator considers would make the candidate unsuitable for the study.

Study Drug Administration:

1. **The study agent will be administered by 10mg/kg dose** at 2 weeks intervals for the first 3 doses and every 4 weeks thereafter. It is administered IV over a minimum of 1 hour. During the study visit at each dosing the patient will be monitored and routine laboratory testing will be performed according to standard of care. See Appendix A for infusion dosing schedule.

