- Post study follow up phone call with subject conducted at Week 72 and 84.
- Patients who previously received IVIG and with Hep B core IgG positive and Hep B sAB positive will undergo surveillance with Liver function test, Hepatitis Panel and Viral Load every 3 months.

Data Safety Monitoring Plan:

The principal investigator and two independent physicians, designated by the Principal Investigator, will be responsible for the oversight of the data safety monitoring plan. The committee will meet every 6 months to evaluate the rate of unanticipated adverse events. If any

safety signals are identified, recommendations to changes in the protocol or consent will be defined by the committee. Benefit-to-risk assessment will be made in order to determine if the study should continue. The results of these regular meetings will be recorded and disseminated to all participating clinical sites.

Feinstein Biostatistics Unit BUDDY System: Data Management

The Biostatistics Unit (BU), within The Feinstein Institute for Medical Research (FIMR), provides state-of-the-art statistical and data management support to the research investigators at Northwell Health as well as other medical research institutions in the New York area. Its staff of ten PhD and Masters level statisticians and two senior applications programmers has extensive experience in the design, data management, and analysis of hundreds of clinical research projects, including over 250 clinical trials. Primary expertise is in clinical trials, diagnostic testing and screening, the development of predictive models for prognosis, and development of protocols and grant applications.

The Biostatistics Unit provides data management support through its “BUDDY” system (“Biostatistics Unit Database Designed for You”). BUDDY is a highly customized, secure, HIPAA-compliant, web-based database application. It is particularly suited to studies with longitudinal and relational data structures, especially clinical trials. The cost of database development may vary depending upon features requested by the user, including, but not limited to: case report form development, number of unique data screens, transfer of data between another system and BUDDY, data validation checks between screens, image file storage, special queries or reports, translation of adverse event descriptions into MedDRA, and data submission tracking.

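### Two hepatitis B viral load intervals, 3 months and 2 months, are set for the same enrolled patients, and the longer one falls short of the condition on which they are admitted

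*Combined protocol and SAP*

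**What the plan says.** Four places in the combined protocol and SAP bear on this.

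- **Exclusion Criteria, item 16 (hepatitis B note).** Patients with past IVIG, positive core IgG and positive surface antibody "are allowed to be enrolled but additional safety monitoring procedures must be followed on these patients". The note then directs the site: "please see Appendix C: Follow Up Assessments".
- **Study Procedures & Assessments, near the end.** The same group, defined by past IVIG and both antibodies, "will undergo surveillance with Liver function test, Hepatitis Panel and Viral Load every 3 months".
- **Appendix C, Follow Up Assessments.** The population is introduced as "For subjects who have had IVIG in the past and with Hep B core IgG pos and Hep B sAB pos", and the rule is "HBVDNA testing must be done every 2 months". A further test is required if either transaminase rises beyond 2.5 times the upper limit of normal (ULN) while the patient is on study. This list sits below the heading "Required Actions and Follow up Assessments following ANY Liver Stopping Event".
- **Appendix A (Study Schedule).** There is no row for HBV DNA or any other hepatitis B test.

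**The concern.** One group of patients has two intervals for one test, and nothing says which takes precedence. The eligibility note makes the Appendix C monitoring a condition of entry, so the 3-month rule in Study Procedures is less than that condition requires. Study Procedures neither refers to Appendix C nor mentions the transaminase trigger, so a site that builds its calendar from that section could miss both parts of the Appendix C rule.

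Two features make the mismatch easy to overlook. The 2-month sentence lies under a heading about liver stopping events and can be misread as applying only after one. The visit schedule, which is where a coordinator would look, is silent.

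What is at stake is the safety surveillance of patients with serological markers of hepatitis B while they receive the study agent, not the efficacy analysis.

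**Working it through.** **Is it the same population and the same test?**

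| | Study Procedures & Assessments | Appendix C, Follow Up Assessments |
|---|---|---|
| Prior IVIG | yes | yes |
| Core IgG positive | yes | yes |
| Surface antibody positive | yes | yes |
| Test | viral load, with liver function tests and hepatitis panel | HBV DNA |
| Interval | 3 months | 2 months |
| Extra test if ALT or AST exceeds 2.5×ULN | not mentioned | required |

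The populations are identical. Viral load, listed beside a hepatitis panel for patients selected on hepatitis B serology, is read here as HBV DNA.

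**Does the 2-month rule apply only after a liver stopping event?** The heading suggests it might, but three points are against it.

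1. The eligibility note sends every enrolled patient of this type to that list, with no liver event required.
2. The same sentence sets a trigger at 2.5×ULN during the study. Every stopping criterion in Appendix C requires ALT of at least 3×ULN, so a 2.5×ULN trigger would make little sense if it started only after a stopping event.
3. Appendix C repeats that trigger among the increased monitoring criteria for patients who continue treatment.

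**How many scheduled tests separate the two rules?** The inputs are the last infusion at week 64 and total follow-up of 84 weeks, both from Study Design. The documents do not say when the surveillance ends, so both horizons are shown.

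One calendar month = 365.25 / 12 / 7 = 4.348 weeks. Tests after baseline = whole part of (months of follow-up / interval).

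| Horizon | Months | Every 3 months | Every 2 months | Shortfall |
|---|---|---|---|---|
| Week 64 | 64 / 4.348 = 14.72 | 14.72 / 3 → 4 | 14.72 / 2 → 7 | 3 |
| Week 84 | 84 / 4.348 = 19.32 | 19.32 / 3 → 6 | 19.32 / 2 → 9 | 3 |

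With 4-week months the counts are 5 against 8 to week 64 (16 months) and 7 against 10 to week 84 (21 months). The shortfall is again 3.

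Gap between scheduled tests: 3 × 4.348 = 13.0 weeks against 2 × 4.348 = 8.7 weeks, a difference of about 4.3 weeks.

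**The case against.** The case for treating this as a minor wording slip is fair in several respects. Testing every 2 months satisfies both sections, so no site is forced into a deviation. The only text that admits these patients points to the stricter rule, so a site that tests every 3 months has overlooked that pointer. The eligibility table admits such patients only with negative surface antigen and negative PCR. ALT and AST are drawn at every infusion visit. The transaminase trigger appears twice in Appendix C, and muscle disease may set it off often, so the counts above are of scheduled tests and not of all HBV DNA tests. The week 84 figures are hypothetical, since Study Design describes telephone contact at weeks 72 and 84. Other conditional tests, such as monthly IgG, have no row of their own in Appendix A either.

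All of this limits the size of the problem, but it does not remove the conflict. Appendix C requires the scheduled test in addition to the triggered one, and Study Procedures omits the trigger. Appendix C itself acknowledges that transaminases in this population can be abnormal because of muscle injury, so they are a less specific liver signal here; a scheduled viral load does not depend on interpreting them. The point about Appendix A stands in part: a new row is helpful, not essential.

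**Conclusion.** The inconsistency is real and should be corrected. Study Procedures & Assessments sets a viral load interval about 4.3 weeks longer than the one tied to enrolment, which means 3 fewer scheduled tests per affected patient (4 instead of 7 to week 64; 6 instead of 9 if surveillance were to run to week 84).

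This rests on reading viral load as HBV DNA and on a site following Study Procedures alone. The size of the subgroup is not given; it is probably small and could be 0 of 30. The documents do not show how much harm, if any, the longer gap would cause. The primary analysis and the sample size are unaffected.

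**What to change.** 1. In Study Procedures & Assessments, change the viral load interval to 2 months, add the trigger for ALT or AST above 2.5×ULN, and refer to Appendix C. The liver function tests and hepatitis panel in that sentence can stay at 3 months. If the sponsor prefers 3 months for viral load, it should justify that choice and amend Appendix C, so that one interval stands everywhere.
2. In Appendix C, state that 2-monthly HBV DNA testing is routine surveillance for this subgroup from Day 0, not only follow-up after a liver stopping event, and say when it ends.
3. Preferably, add an HBV DNA row for this subgroup to Appendix A at existing visits, for example weeks 8, 16, 24, 32, 40, 48, 56 and 64. That is 64 / 8 = 8 draws at 8-week spacing, slightly tighter than the 8.7 weeks that 2 calendar months imply.

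The cost is protocol wording, one schedule row, and 7 − 4 = 3 extra tests per affected patient over 64 weeks, or 8 − 4 = 4 with the 8-weekly row, at visits where blood is already drawn.
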